5.0 Special Considerations

5.1 Health Insurance Portability and Accountability Act (HIPAA)

N/A

5.2 Family Educational Rights and Privacy Act (FERPA)

N/A

5.3 Code of Federal Regulations Title 45 Part 46 (Vulnerable Populations)

N/A

A. Special Populations

N/A

5.4 General Data Protection Regulation (GDPR)

N/A

5.5 NJ Access to Medical Research Act (Surrogate Consent)

N/A

6.0 Data Management Plan

6.1 Data Analysis

We will use linear regressions to assess the associations between experimental conditions and various outcomes described above. We will add the interaction terms to the regression models to test the interactive effects of tobacco-use status and the experimental effect. We will also provide estimates of participant characteristics and assess their even distributions across conditions.

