1.0 Research Design

1.1 Purpose/Specific Aims

The overall purpose of this study is to assess the influence of e-cigarette advertisements (ads) and their high-impact ad features (flavor features, reduced exposure messages, and FDA-authorized claims) on perceptions and intentions of using e-cigarettes among young adults (ages 18-30). Using two randomized between-subject experiments in an online survey, the main goal of the first experiment is to examine the effect of viewing different flavor features (flavor name, product color that coincides with flavor name, flavor image, flavor sensation descriptor, and flavor choice claim) on self-reported e-cigarette use perceptions and use intentions. The main goal of the second experiment is to examine the effect of viewing different e-cigarette marketing claims suggesting harm reduction (reduced exposure claim, FDA-authorization claims) on self-reported e-cigarette use perceptions and use intentions.

A. Objectives

Objective 1: To assess if exposure to e-cigarette ads with flavor features and reduced harm claims will result in greater positive perceptions and increased e-cigarette use intentions than exposure to e-cigarette ads without these features.

B. Hypotheses / Research Question(s)

Hypothesis 1: Exposure to e-cigarette ads with flavor features and reduced harm claims will result in greater positive perceptions and increased e-cigarette use intentions than exposure to e-cigarette ads without these features.

Hypothesis 2: The positive effect of exposure to e-cigarette ads with flavor features on e-cigarette use intentions will be moderated by participants' tobacco-use status.

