1.5 Sample Size Justification

There will be 3,000 subjects enrolled in the study. Our previous studies using a similar study design examining the influence of e-cigarette marketing features used sample sizes of approximately 3,000 to obtain sufficient power for detecting differences in product perceptions and use interest with small to moderate effect sizes. Other studies have shown that 500 subjects per group (6 randomizing conditions) will provide sufficient power to detect differences in perceptions and use intentions after viewing varying ad features as well as the moderating effect of tobacco-use status on those associations.

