1.6 Study Variables

A. Independent Variables, Interventions, or Predictor Variables

The predictor variable will be subjects' conditions they are assigned to for the two experiments.

B. Dependent Variables or Outcome Measures

For both experiments, four groups of outcome measures will be used. See the Survey attachment for detailed measures

1. Ad appeal
2. E-cigarette use intentions
3. E-cigarette risk perceptions
4. E-cigarette outcome expectancies

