4.0 Subject Considerations

4.1 Subject Selection and Enrollment Considerations

A. Method to Identify Potential Subjects

Subjects will be registered Qualtrics study panel members. Potential subjects will initially review a brief description of the study (see Attachment A), and those who are interested in participating will proceed to the eligibility screening questions assessing their age and tobacco use history (see Attachment B). If eligible, they will then be directed to the online consent form (see Attachment C).

B. Recruitment Details

In Spring 2025, subjects will be recruited via Qualtrics' online study panels. Potential subjects who see and choose to complete our task (i.e., study) will complete it using Qualtrics' survey platform. Recruitment is anticipated to take approximately three weeks.

C. Subject Screening

▪ Inclusion Criteria

Three groups of young adult subjects (ages 18-30) will be included in the study. The first group is those who are exclusive cigarette smokers (n=1000), defined as those who have smoked at least 100 cigarettes in their lifetime and have smoked at least one cigarette in the past 30 days but have not used e-cigarettes in the past 30 days. The second group is those who are dual users of cigarettes and e-cigarettes (n=1000). Those in this group have smoked more than 100 cigarettes in their lifetime and have smoked a cigarette and also used an e-cigarette in the past 30 days. The third group is those who are non-tobacco users (n=1000), defined as those who have never used any tobacco product before or have never "regularly" used tobacco products before and are currently not using any tobacco products (in the past 30 days).

▪ Exclusion Criteria

Any subjects not meeting the inclusion criteria described in 4.1.C will be excluded from the study. Individuals will be further excluded if they do not provide consent to participate in the study.

D. Privacy Protections

Our survey will be publicized via Qualtrics (see Attachment D) to their registered study panel members. The screening questions (see Attachment B) pertain solely to demographics and tobacco use history and do not request any personally identifiable information. The PI will not receive the responses to the screening questions from Qualtrics if the subjects do not agree with the consent form or do not complete the survey.

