Title: High Impact E-cigarette Advertisement Features

NCT06704295

Document Date: 11/01/2024

Data Analysis Plan

We will use linear regressions to assess the associations between experimental conditions and various outcomes described above. We will add the interaction terms to the regression models to test the interactive effects of tobacco-use status and the experimental effect. We will also provide estimates of participant characteristics and assess their even distributions across conditions.

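### Tobacco-use group is not named as a covariate in the main-effect regressions, and no estimate is tied to Hypothesis 1, so a nearly free gain in precision is left unsecured

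*Protocol*

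**What the plan says.** The analysis text is three sentences, the same in Protocol 6.1 and the SAP. The main-effect analysis is: "We will use linear regressions to assess the associations between experimental conditions and various outcomes described above". Moderation follows: "We will add the interaction terms to the regression models to test the interactive effects of tobacco-use status and the experimental effect". Participant characteristics are to be described and compared across arms: "We will also provide estimates of participant characteristics and assess their even distributions across conditions".

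Protocol 1.6 A names assigned condition and nothing else: "The predictor variable will be subjects' conditions they are assigned to for the two experiments". Section 1.6 B lists four outcome groups: ad appeal, use intentions, risk perceptions and outcome expectancies.

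Hypothesis 1 (Protocol 1.1 B) is stated without restriction to any tobacco-use group: "Hypothesis 1: Exposure to e-cigarette ads with flavor features and reduced harm claims will result in greater positive perceptions and increased e-cigarette use intentions". Only Hypothesis 2 refers to tobacco-use status.

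Protocol 4.1 C fixes recruitment at 1,000 exclusive smokers, 1,000 dual users and 1,000 non-users of tobacco. Under 4.1 A, potential subjects "proceed to the eligibility screening questions assessing their age and tobacco use history" before they reach consent, the survey and the randomized ads. Section 1.3 does not mention stratifying the randomization by group.

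**The concern.** Tobacco-use group is part of the design: its distribution is set by quota, it is known for everyone before exposure, and it separates people partly by whether they used e-cigarettes in the past 30 days. Such a variable may well predict intentions to use e-cigarettes and perceptions of them. If it does, leaving it out of the main-effect model puts between-group variation into the residual and widens every confidence interval for a condition contrast.

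The plan does not say that the main-effect models are unadjusted; it is silent. Nor does it say whether Hypothesis 1 is tested by:

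- a condition coefficient from a model without tobacco-use status;
- a coefficient from the interaction model; or
- an average over the three groups.

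These differ in precision, and one of them differs in meaning. With ordinary dummy coding, the condition coefficient in the interaction model is the effect in the reference tobacco-use group alone. The choice should be fixed before the data are seen.

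Validity is not at stake. Randomization makes the unadjusted contrast unbiased.

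**Working it through.** **Inputs from the documents.** Total 3,000 and 500 per condition (Protocol 1.5); six conditions in each experiment (1.3); three groups of 1,000 (4.1 C). The counts agree: 3,000/6 = 500 and 3 × 1,000 = 3,000. Section 1.5 claims "sufficient power for detecting differences in product perceptions and use interest with small to moderate effect sizes" but gives no alpha, power, effect size or SD, so there is no power figure to reproduce.

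**Assumptions.** Two-sided alpha 0.05, 80% power, outcome SD 1. R² is the share of within-condition outcome variance explained by tobacco-use group. The range starts at 0. Its top comes from assumed group means of 0, 0.7 and 1.5 within-group SDs: between-group variance 0.3756, so R² = 0.3756/1.3756 = 0.273.

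**Formulas.** For one contrast of 500 versus 500:

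- SE = √(2/500) × √(1 − R²); unadjusted, 0.0632.
- Detectable difference = (1.960 + 0.842) × SE = 2.802 × SE.
- Power at difference d = Φ(d/SE − 1.960).
- Equivalent total N = 3,000/(1 − R²).

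| R² | Detectable difference (SD) | Power at 0.15 SD | Power at 0.20 SD | Equivalent N |
|---|---|---|---|---|
| 0 (also unadjusted) | 0.177 | 66.0% | 88.5% | 3,000 |
| 0.02 | 0.175 | 66.9% | about 89% | 3,061 |
| 0.05 | 0.173 | 68.2% | 90.1% | 3,158 |
| 0.10 | 0.168 | 70.5% | 91.5% | 3,333 |
| 0.273 | 0.151 | 79.4% | 96.0% | 4,127 |

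Unadjusted power at 0.30 SD is 99.7%.

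**Cost when group explains nothing.** Two of 3,000 − 6 = 2,994 residual degrees of freedom.

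**Simulation check.** 3,000 runs per scenario; three groups of 1,000, six arms of 500, true effect 0.15 SD. Mean estimates were 0.150 to 0.152 for all three estimators. Empirical SEs:

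| R² | Unadjusted | Group as covariate | Average of group-specific effects |
|---|---|---|---|
| 0 | 0.0628 | 0.0629 | 0.0629 |
| 0.051 | 0.0629 | 0.0614 | 0.0614 |
| 0.098 | 0.0636 | 0.0603 | 0.0604 |
| 0.273 | 0.0642 | 0.0545 | 0.0546 |

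Simulated power followed the formula. At R² = 0.273 it was 65.8% unadjusted, 79.0% with the covariate and 78.8% with the average.

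**Effects that differ by group.** Hypothesis 2 expects moderation, so this case was simulated too, at the top of the R² range. The covariate model and the averaged interaction model gave the same mean and the same SE: 0.0625, against 0.0755 unadjusted.

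**If the reference-group coefficient were used instead.** About 1,000/6 = 167 people per condition contribute. At R² = 0, SE = √(2/166.7) = 0.1095, the detectable difference is 2.802 × 0.1095 = 0.307 SD, and power at 0.20 SD is 45% rather than 88.5%.

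**The case against.** **Power is already adequate.** At 0.20 SD and above it is, and the claim in Protocol 1.5 holds if small means about 0.20 SD. This stands, and it caps the severity. The gain counts below that size. Experiment 1 builds its ads by adding one feature at a time, and Protocol 1.2 and 1.4 ask which features or combinations matter most; differences between neighbouring ads may be smaller than 0.20 SD.

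**The interaction model already includes group.** Coded conventionally, it does, and averaging its three group-specific effects gives the same precision as adding the covariate. But the plan does not say that this average will be formed or that it tests Hypothesis 1. The gap is therefore largely one of wording, which is why the remedy is cheap.

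**The variance share is invented.** It is an assumption, and the larger figures depend on it entirely. Between R² = 0.02 and 0.10, power at 0.15 SD rises only to 66.9–70.5%. The gain may differ across the four outcome groups and be near zero for some. At zero, however, the cost is also close to zero.

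**500 versus 500 may not be the Hypothesis 1 contrast.** In experiment 1 the hypothesis could mean Conditions 2–6 pooled against Condition 1. Then the unadjusted SE is √(1/500 + 1/2,500) = 0.0490, the detectable difference 0.137 SD, and power at 0.15 SD about 86%. This is a fair reading, and the 66% baseline applies only to pairwise contrasts. The proportional gain is unchanged: 0.137 × √0.90 = 0.130 SD at R² = 0.10.

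**Conclusion.** The concern holds, as a minor one. The plan names no covariate for the main-effect models and ties no estimate to Hypothesis 1, although a design variable that may predict the outcomes is already recorded before randomization.

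Adjustment multiplies the SE by √(1 − R²): no reduction at R² = 0, about 5% at 0.10, and about 15% at 0.273. The range rests on an assumed R², since the documents report no outcome variance by group; the power figures further assume two-sided 0.05 and pairwise contrasts. No bias is alleged, and the study is not underpowered at 0.20 SD.

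**What to change.** In Protocol 6.1 and the SAP, state that:

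1. Every main-effect model in both experiments includes tobacco-use group as a three-level covariate, that the adjusted condition contrast tests Hypothesis 1, and that the interaction is tested as a separate step. An equivalent statement is that Hypothesis 1 is tested by the equally weighted average of the three group-specific condition effects from the interaction model.
2. Optionally, the comparison of participant characteristics across conditions is descriptive and will not be used to choose covariates. The plan does not propose such selection; this only closes the door on it.

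The cost is one or two sentences and 2 degrees of freedom per main-effect model. Group is already collected at screening, so no new items, data or participants are needed.

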
1.3 Research Design and Methods

To assess the impact of those features and claims, we will administer two separate randomized experiments through this online survey project where subjects will be assigned to one of six e-cigarette ad conditions (experiment 1) and one of the six e-cigarette ad conditions (experiment 2). The survey will include a series of questions about subjects' sociodemographic backgrounds, health

conditions, tobacco use history and dependence, and tobacco use environment. Static images of mock e-cigarette ads will be created based on publicized ads in brand company websites and emails.

A. Research Procedures

Young adult subjects will be recruited from online study panels administered by Qualtrics. Qualtrics will send out a brief description of the study for young adult recruitment (see Attachment A). Those who are interested in participating will first receive a screening survey (see Attachment B) to ensure eligibility. Those who are eligible will move on to the informed consent page (see Attachment C) and those who agree with the consent will proceed to complete the study survey (see Attachment D). In the survey, subjects will first answer a series of questions about demographics, health conditions, tobacco use history and dependence, and tobacco use environment. Afterward, for experiment 1, subjects will be randomly assigned to one of six conditions where they will be exposed to an e-cigarette ad either featuring an e-cigarette product that may or may not include high-impact flavor features. Condition 1 (control condition) will not include any high-impact flavor features and conditions 2-6 will include at least one high-impact flavor feature (flavor name, product color that coincides with flavor name, flavor sensation descriptor, and flavor choice claim). Attachment E includes stimuli for each experimental condition. Each ad will also include other ad features (e.g., nicotine warning label, generic marketing claim) to help increase ad authenticity. The conditions are:

- Condition 1: Black product with tobacco flavor name
- Condition 2: Black product with strawberry flavor name
- Condition 3: Colorful (strawberry color) product with strawberry flavor name
- Condition 4: Colorful (strawberry color) product with strawberry flavor name + strawberry image
- Condition 5: Colorful (strawberry color) product with strawberry flavor name + strawberry image + strawberry flavor sensation descriptor

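### No standard-error method is specified for the condition-by-tobacco-use models; the default pooled variance would misstate status-specific and some pairwise interaction errors if outcome spread differs by group

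*Protocol*

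**What the plan says.** Protocol 6.1 and the SAP's Data Analysis Plan use the same text. Outcomes are regressed on experimental condition by linear regression, and then: "We will add the interaction terms to the regression models to test the interactive effects of tobacco-use status and the experimental effect". Neither document mentions a residual-variance structure, robust standard errors, weighting or a check of residuals.

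The moderator is built into recruitment. Protocol 4.1 sets three equal quotas: "exclusive cigarette smokers (n=1000"), "dual users of cigarettes and e-cigarettes (n=1000") and, for the last, "The third group is those who are non-tobacco users (n=1000"). Hypothesis 2 in protocol 1.1 states that the effect of flavor-feature ads on use intentions "will be moderated by participants' tobacco-use status". Protocol 1.5 claims enough power for that moderation as well as for the condition effects. Protocol 1.6 lists four outcome groups (ad appeal, use intentions, risk perceptions, outcome expectancies) and leaves the measures to the survey attachment.

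**The concern.** The quota groups are defined by the behavior that the use-intention outcome asks about. People who use no tobacco may cluster at the bottom of an intention scale, while people who already vape and smoke may spread across it. If so, the residual variance is not common to the 18 condition-by-status cells. A default fit would still estimate one variance and apply it everywhere.

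The affected quantities are ones that the interaction model prints. With ordinary reference coding, once the interactions are in, each condition coefficient is the effect in the reference status group, and each interaction coefficient is a difference between two groups. These are the estimates needed to say who responds to the ads, which is the substance of Hypothesis 2. Intervals that are too wide for non-users and too narrow for a more variable user group would distort that reading.

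**Working it through.** **The plan's own figure.** Protocol 1.5 states "There will be 3,000 subjects enrolled in the study" and "500 subjects per group (6 randomizing conditions) will provide sufficient power". The division agrees: 3,000/6 = 500. The power claim cannot be reproduced, because no alpha, SD, effect size or power value is given. Assuming two-sided 5%, 80% power and SD 1, the detectable difference is 2.80 × sqrt(2/500) = 0.18 between two full conditions. It is 2.80 × sqrt(2/167) = 0.31 within one status group and 2.80 × sqrt(4/167) = 0.43 for a pairwise interaction.

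**Inputs.**
- From the documents: 1,000 per status group (4.1) and six conditions (1.3), so 1000/6 ≈ 167 per cell.
- Assumed: equal allocation within each status group (1.3 says only "subjects will be randomly assigned to one of six conditions"), two-sided 5%, and group SDs. SDs are always listed as non-users/exclusive smokers/dual users.

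**Formulas.** Let s_p² be the mean of the three group variances, which is what the pooled fit estimates with equal groups.
- Status-specific contrast: model SE / true SE = s_p/s_g.
- Pairwise interaction contrast: model SE / true SE = sqrt(2 s_p²/(s_g² + s_h²)).
- True type I error = 2 × (1 − Φ(1.96 × ratio)).
- Power for an effect of 0.31 within-group SD = Φ(0.31/sqrt(2/167) − 1.96 × ratio) = Φ(2.83 − 1.96 × ratio).

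**SDs 0.8/1.0/1.2.** s_p² = (0.64 + 1.00 + 1.44)/3 = 1.027, so s_p = 1.013. The status-specific ratios are 1.27, 1.01 and 0.84. The interaction ratios are 1.12, 0.99 and 0.92.

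**SDs 0.6/1.2/1.2.** s_p² = (0.36 + 1.44 + 1.44)/3 = 1.08, so s_p = 1.039. The status-specific ratios are 1.73, 0.87 and 0.87. The interaction ratios are 1.10, 1.10 and 0.87.

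| True type I error at nominal 5% | Equal SDs | 0.8/1.0/1.2 | 0.6/1.2/1.2 |
|---|---|---|---|
| Effect in non-users | 5.0% | 1.3% | 0.07% |
| Effect in exclusive smokers | 5.0% | 4.7% | 9.0% |
| Effect in dual users | 5.0% | 9.8% | 9.0% |
| Non-user vs smoker interaction | 5.0% | 2.8% | 3.2% |
| Non-user vs dual-user interaction | 5.0% | 5.2% | 3.2% |
| Smoker vs dual-user interaction | 5.0% | 7.2% | 9.0% |
| Power in non-users, 0.31 SD | 81% | 64% | 29% |

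**A bounded item.** An assumed 5-point item with 75% of non-users at the lowest score gave SDs of 0.93/1.38/1.35. Over 20,000 simulated trials the status-specific errors were 0.9%/7.7%/7.4%. The interaction errors, in the table's order, were 3.9%, 3.6% and 7.4%.

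**What is protected.** The equally weighted average of the three status-specific effects has variance (1/9) × Σ 2s_g²/n = (1/3) × 2s_p²/n, which is what the pooled model uses. In simulation the average condition effect ran at about 4.9%. The joint 10-df interaction test ran at about 5.3% to 6.3% over the unequal-SD sets tried.

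**After the change.** In simulation, HC3 errors gave 4.9% to 5.2% in every status group, with equal and with unequal SDs. Cell-specific variances gave 4.8% to 5.2% for every status-specific and pairwise contrast. Power in non-users for 0.31 SD returns to about 81%.

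**The case against.** The strongest reply is that the plan makes no wrong choice; it is silent. The text says linear regressions, in the plural, over several outcomes and two experiments, and a fit with robust errors would satisfy it. A reader might infer that the plan commits to a shared residual variance. It does not; that is only the default when nothing else is specified. This stands, and the point is therefore one of omission. Silence does, however, leave the choice of standard error open until results are seen.

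Second, no group SDs are given, and scale length and scoring are in an attachment. The floor argument is natural for use intentions and weaker for the other three outcome groups. The documents also give some reason for doubt. Protocol 4.1 admits non-users with past, non-regular tobacco use. Protocol 1.4 reports interviews in which young adults who do not use tobacco found the ads appealing and expressed interest. This stands too: unequal spread is plausible, not shown.

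Third, the tests closest to the plan's wording barely move, and the plan does not name status-specific effects. This limits the reach but does not remove the point, because the interaction model reports those effects and Hypothesis 2 cannot be interpreted without them.

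**Conclusion.** The point holds as a conditional one. If outcome spread differs by tobacco-use status, the default fit gives standard errors that are too wide in the low-variance group and too narrow in the high-variance group, and neither document guards against it. Under the two assumed SD sets, type I error for status-specific effects runs from 0.07% to 9.8% and for pairwise interactions from 2.8% to 9.0%. Not every contrast is distorted: at 0.8/1.0/1.2, the exclusive-smoker effect (4.7%) and the non-user versus dual-user interaction (5.2%) are close to nominal.

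Two stronger readings are not supported. A reader might infer that false effects in users will be declared and true effects in non-users missed. That depends on SDs the documents do not give, and it vanishes if they are equal. A reader might also infer that the overall tests of Hypothesis 1 or 2 are invalid. With equal quotas and about equal allocation, the average condition effect is protected and the joint interaction test shifts by little more than one percentage point.

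**What to change.** In protocol 6.1 and the SAP, add one sentence: all regression coefficients, status-specific condition effects, interaction contrasts and Wald tests use heteroscedasticity-consistent (HC3) standard errors. Report the status-specific condition effects with those errors.

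Do not describe a separate residual variance per status group as equivalent. That model still assumes equal variance across the six conditions within a group. An ad that lifts non-users off the scale floor would also change their variance, so the assumption could fail under the very mechanism of concern.

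The cost is one sentence in each document and one software option in the packages listed in protocol 2.2. Design, sample size and data collection are unchanged, and with equal variances the loss of efficiency is negligible.

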1.8 Data Collection

A. Primary Data Collection

- **Location:** The survey will be programmed online, via Qualtrics, an online survey platform.
- **Process of Data Collection:** Data collection will be managed by Qualtrics, and young adult subjects will be recruited from Qualtrics' existing study panels.
- **Timing and Frequency:** The survey will be a one-time occurrence estimated to take approximately 20 minutes.
- **Procedures for Audio/Visual Recording:** N/A
- **Study Instruments:** The survey is included with this application (see Attachment D). The study survey will assess tobacco-using history, perceptions about tobacco products and tobacco use, perceptions of e-cigarette ads with various features and claims, intentions perceptions of using the products in these ads, and subject demographics.
- **Ethnographic Studies, Interviews, Or Observation:** N/A
- **Subject Identifiers:** Data will be collected from young adult subjects online who are registered users of Qualtrics survey panels. Qualtrics takes extensive measures to ensure that all registered members' privacy and personal information are treated confidentially and kept secure. For this study, all data will be de-identified and anonymous to the PI and no personal information will be released to the PI. We will set up the Qualtrics survey in a way to not collect subjects' PI addresses using the Anonymous Response features, in order to collect completely anonymous survey responses. At the beginning of the survey, Qualtrics will generate a random Subject ID.

B. Secondary Data Collection

- **Type of Records:** N/A
- **Location:** N/A
- **Inclusion/Exclusion:** N/A
- **Data Abstraction Form(s):** N/A

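### Baseline items asked before the first ad are given no role in the regression models, so estimates in both experiments are valid but less precise than the collected data allow

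*Protocol*

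**What the plan says.** Protocol 1.3 A sets the order of the survey: "subjects will first answer a series of questions about demographics, health conditions, tobacco use history and dependence, and tobacco use environment". Random assignment to an Experiment 1 ad follows that block, and Experiment 2 comes after Experiment 1. The block therefore precedes all ad exposure in both experiments.

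Protocol 1.6 A lists assigned condition as the predictor. Protocol 6.1 has three sentences: linear regressions of the outcomes on condition, interaction terms with tobacco-use status, and "We will also provide estimates of participant characteristics and assess their even distributions across conditions". The SAP repeats the same three sentences and adds nothing. Neither document names an adjustment covariate or says what would follow if a characteristic were unevenly distributed.

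Tobacco-use status is the one baseline variable that enters a model, as the moderator for Hypothesis 2. Protocol 4.1 C defines it by eligibility, with 1,000 subjects in each of three groups.

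On size, Protocol 1.5 states "There will be 3,000 subjects enrolled in the study" and relies on other studies for the claim that "500 subjects per group (6 randomizing conditions) will provide sufficient power to detect differences in perceptions and use intentions", and also for power to detect moderation by status.

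**The concern.** Answers given before exposure cannot be affected by the ad. If they predict intentions or perceptions, putting them in the model removes outcome variance and narrows the intervals without biasing the randomized comparison. Comparing their distributions across conditions leaves every estimate and standard error as it was.

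Two things are at stake. The first is precision, in the main effects of both experiments and in the Hypothesis 2 interactions. Status is already in the interaction models, so further gain there can come only from items that vary within a status group. The second is pre-specification: with four outcome groups and two experiments, a plan that names no covariates leaves any later adjustment to be decided after the data are seen.

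**Working it through.** **The plan's own figure.** 6 conditions × 500 = 3,000, which agrees with Protocol 1.5. The power statement cannot be reproduced. It speaks of "sufficient power for detecting differences in product perceptions and use interest with small to moderate effect sizes" but gives no alpha, power, SD or numeric effect size.

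**Inputs from the documents.** 500 per condition (1.5); three status groups of 1,000 (4.1 C), hence 1,000 / 6 ≈ 166.7 per condition-by-status cell.

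**Assumed inputs.** Two-sided alpha 0.05; 80% power; SD 1 within tobacco-use status; share of within-status outcome variance explained by the covariates, R², from 5% to 30%. No R² is given in the documents.

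**Formulas.** With 1.960 + 0.842 = 2.802:

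- Two conditions: 2.802 × √(2/500) × √(1 − R²)
- One Hypothesis 2 contrast (a difference of two differences, four cells): 2.802 × √(4/166.7) × √(1 − R²)
- Equivalent total sample: 3,000 / (1 − R²)

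**Results.**

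| R² | SE ratio | Two conditions (SD) | One H2 contrast (SD) | Equivalent N |
|---|---|---|---|---|
| 0 | 1 | 0.177 | 0.434 | 3,000 |
| 5% | 0.975 | 0.173 | 0.423 | 3,158 |
| 10% | 0.949 | 0.168 | 0.412 | 3,333 |
| 20% | 0.894 | 0.158 | 0.388 | 3,750 |
| 30% | 0.837 | 0.148 | 0.363 | 4,286 |

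The SE ratio is the same in both columns, so main effects and interactions gain in the same proportion.

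**If the items predict only among users.** Eligibility fixes past-30-day e-cigarette use at zero for exclusive smokers and non-users, and past-30-day smoking at zero for non-users. Dependence items have little or no meaning for the 1,000 non-users. Suppose the covariates explain 20% in the two user groups and nothing in non-users:

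- Average residual variance = (1,000 × 1 + 2,000 × 0.8) / 3,000 = 0.867. Two conditions: 0.177 × √0.867 = 0.165 SD, instead of 0.158.
- User-versus-non-user contrast: 2.802 × √[(2/166.7) × (1 + 0.8)] = 0.412 SD, instead of 0.388. The SE falls about 5%, not 11%.

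**Cost in degrees of freedom.** Twenty covariates raise the estimated residual variance by a factor of 2,994 / 2,974 = 1.007 in the main-effect model, about 0.7%. An R² above about 1% is therefore a net gain.

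**The case against.** The strongest reply is that this is a preference about efficiency. The unadjusted comparison is unbiased and its intervals are valid. The size of the gain rests wholly on an assumed R², and at 5% to 10% the two-condition figure moves only from 0.177 to 0.173–0.168 SD. All of that stands. It bears on how much the point matters, not on whether the change is worth making, since the categories of item are already collected.

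Several stronger readings are tempting, and the documents do not support them:

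- A reader might infer that the planned analysis is biased, or that adjustment is ruled out. Neither follows. That the items serve only for description and a balance check is read from silence; the plan does not forbid adjustment, and does not say that an imbalance would trigger it.
- A reader might infer that Hypothesis 2 gains most because its cells are small. The fall is larger in SD units, but the proportional gain is the same for equal R². For contrasts involving non-users it may be smaller, as shown above.
- A reader might infer that the balance check is pointless because any imbalance must be chance. That holds for everyone randomized. Protocol 4.7 lets subjects quit at any time, Protocol 4.1 D withholds the screening responses of those who do not complete, and no analysis set is defined. If completers are analyzed, the comparison by condition is a reasonable check on assignment faults and drop-out.
- A reader might infer that the survey's items on "perceptions about tobacco products and tobacco use" (Protocol 1.8 A) could serve as a baseline score. Their timing is not given, and the pre-ad block in 1.3 A does not list them. Moving them would alter the survey and might interact with the claims shown in Experiment 2.

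The reply is also right that Protocol 1.3 A gives categories only. The individual questions are in Attachment D, which is not among the documents reviewed, so a list of specific items cannot be verified here.

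**Conclusion.** The point holds as a gap in efficiency and pre-specification that affects both experiments. It is not an error that invalidates any comparison. Under the assumptions stated, adjustment would cut standard errors by about 3% to 16%, equivalent to enrolling about 3,158 to 4,286 subjects instead of 3,000. The lower part of that range is the more cautious expectation for contrasts that involve non-users, because some of the likeliest predictors do not vary in that group. The detectable Hypothesis 2 contrast without adjustment, 0.434 SD, shows that precision for moderation is limited. Adjustment helps there but does not transform it.

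**What to change.** In Protocol 6.1 and the SAP:

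1. Before data are seen, fix one short covariate list drawn from the items actually asked ahead of the first ad, matched to Attachment D, and the same for all outcomes.
2. Enter that list together with tobacco-use status in the main-effect and interaction models of both experiments.
3. State status-specific coding, for example zero for non-users on frequency and dependence items. A dependence score left blank could otherwise drop the non-users from a complete-case regression.
4. Keep the table of characteristics by condition as description and as a check on randomization and drop-out. State that it will not be used to select covariates.

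The cost is wording and a coding rule. No question needs to be added or moved, and the loss of degrees of freedom is negligible at this sample size.
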